4.3 Packaging and Labeling

Enzalutamide used in this study will be prepared, packaged, and labeled, and final release under the responsibility of qualified staff at Astellas US Technologies, Inc (AUST) or designee in accordance with AUST Standard Operating Procedures (SOPs), Good Manufacturing Practice (GMP) guidelines, ICH GCP guidelines, and applicable local laws/regulations.

Enzalutamide capsules are packaged in a white, opaque, high-density polyethylene (HDPE) bottles. Each bottle will bear a label conforming to regulatory guidelines, Good Manufacturing Practice and local laws and regulations which identifies the contents as investigational drug.

Site pharmacist or medically qualified staff will dispense the study treatment to each subject in accordance with this protocol.

A qualified person of Astellas Pharma Europe B.V. (APEBV) or Sponsor's designee will perform the final release of the medication according to Directive 2003/94/EC annex 13.

4.4 Study Drug Handling

Current ICH GCP Guidelines require the Investigator to ensure that study drug deliveries from the Sponsor are received by the Investigator/or designee and

- that such deliveries are recorded,
- that study drug is handled and stored according to labeled storage conditions,
- that study drug with appropriate expiry/retest and is only dispensed to study subjects in accordance with the protocol, and
- that any unused study drug is returned to the Sponsor.

Drug inventory and accountability records for the study drugs will be kept by the Investigator/or designee. Study drug accountability throughout the study must be documented and reconciled. The following guidelines are therefore pertinent:

- The Investigator agrees not to supply study drugs to any persons except the eligible subjects in this study in accordance with the protocol.
- The Investigator or designee will keep the study drugs in a pharmacy or other locked and secure storage facility under controlled storage conditions, accessible only to those authorized by the Investigator to dispense these test drugs.
- A study drug inventory will be maintained by the Investigator or designee. The inventory will include details of material received and a clear record of when they were dispensed and to which subject.
- At the conclusion or termination of this study, the Investigator or designee agrees to conduct a final drug supply inventory and to record the results of this inventory on the Drug Accountability Record. It must be possible to reconcile delivery records with those of used and/or returned medication. Any discrepancies must be accounted for and documented. Appropriate forms of deliveries and returns must be signed by the site staff delegated this responsibility.

- The site must return study drug to the Sponsor or designee at the end of the study or upon expiration unless permission to destroy the study drug at the site is granted by the Sponsor.

4.5 Blinding

This section is not applicable as this is an open-label study.

4.6 Assignment and Allocation

Assignment will be performed via Interactive Response Technology (IRT). IRT will be used for the management of enrollment, screening, subject tracking and clinical supplies. Specific procedures for assignment through the IRT are contained in the study procedures manual.

5 TREATMENTS AND EVALUATION

5.1 Dosing and Administration of Enzalutamide and Other Medication(s)

5.1.1 Dose/Dose Regimen and Administration Period

Subjects will be instructed to take 4 capsules (40 mg each) per day orally. Enzalutamide may be taken with or without food and should be taken as close to the same time each day as possible. The total duration of treatment is 4 months. At the end of the 4-month treatment period, subjects who are assessed as deriving benefit from enzalutamide treatment may continue in the extension period. Subjects in the extension period may continue to receive enzalutamide until they experience bone disease progression per PCWG2 guidelines or soft tissue disease progression per RECIST 1.1, they initiate treatment with another anticancer therapy, continued dosing would lead to undue risk to the subject in the opinion of the Investigator, they meet a discontinuation criterion or the Sponsor terminates the study. The total study drug treatment duration for the extended period will depend on individual clinical benefit to enzalutamide treatment.

Subjects who are continuing to receive clinical benefit from treatment with enzalutamide and have not met any discontinuation criteria may transition to an open label roll-over extension study upon approval of the study protocol at the institution they are receiving treatment at.

5.1.2 Increase or Reduction in Dose of Enzalutamide

Subjects who experience a Grade 3 or higher toxicity that is attributed to enzalutamide and cannot be ameliorated by the used of adequate medical intervention may interrupt treatment with enzalutamide for 1 week or until the toxicity grade improves to Grade 2 or lower severity. Subsequently, study drug dosing may be restarted at the original dose (160 mg/day) or a reduced dose (120 or 80 mg/day) in consultation with the Medical Monitor.

If the adverse event is considered not related to enzalutamide by the Investigator, enzalutamide may be resumed at the same dose.

If the adverse event is considered possibly or probably related to enzalutamide, enzalutamide may be resumed with medical monitor approval either at the same dose or at a reduced dose of 120 or 80 mg/day once daily.

If enzalutamide is co-administered with a strong CYP2C8 inhibitor, the dose of enzalutamide should be reduced to 80 mg once daily. If co-administration of strong CYP2C8 inhibitor is discontinued, the enzalutamide dose should return to the dose used prior to initiation of the strong CYP2C8 inhibitor.

The Sponsor Medical Monitor may be contacted with any questions or concerns on managing dose.

5.1.3 Previous and Concomitant Treatment (Medication and Non-Medication Therapy)

Medication taken within four weeks prior to Screening visit will be collected.

All concomitant medications must be documented at each visit, at the time of discontinuation, and at the 30 day follow-up visit.

The following medications are prohibited during the course of the study:

- Therapies to treat prostate cancer including but not limited to:
 - Cytotoxic chemotherapy
 - Hormonal therapies (e.g., anti-androgens, abiraterone acetate, estrogens; testosterone, dehydroepiandrosterone [DHEA], etc.), 5-alpha reductase inhibitors, ketoconazole;
 - Anticonvulsant substrates of CYP3A4, CYP2C9 or CYP2C19 with a narrow therapeutic index (e.g., carbamazepine, phenytoin, phenobarbital, and primidone are not permitted in this study. Felbamate, vigabatrin, and retigabine are also not permitted for reasons of potential toxicity.
- Note: GnRH analogues (agonists or antagonists), bone-targeting agents, such as bisphosphonates and denosumab, and glucocorticoids are allowed. Palliative radiotherapy is also allowed (provided the subject does not meet discontinuation criteria).
- Any other investigational agent.

There is a potential for enzalutamide to affect exposures to other medicinal products, or for other medicinal products to affect exposure to enzalutamide:

- Strong CYP2C8 inhibitors (e.g., gemfibrozil) or inducers (e.g. rifampicin) are to be avoided. If subject must be co-administered a strong CYP2C8 inhibitor, the dose of enzalutamide must be reduced to 80 mg once daily. If a co-administration of the strong inhibitor is discontinued, the enzalutamide dose should be returned to the dose used prior to initiation of the strong CYP2C8 inhibitor.
- Enzalutamide is a strong inducer of CYP3A4 and a moderate inducer of CYP2C9 and CYP2C19. Uridine 5'-diphospho-glucuronosyltransferase (UGT1A1) may also be induced. Medicinal products with a narrow therapeutic range that are substrates of CYP3A4, CYP2C9, CYP2C19, or UGT1A1 should be used with caution when administered concomitantly with enzalutamide and may require dose adjustment to maintain therapeutic plasma concentrations. Such substrates include, but are not limited to:

- Macrolide antibiotics (e.g. clarithromycin)
- Benzodiazepines (e.g. diazepam, midazolam, alprazolam, triazolam)
- Immune modulators (e.g. cyclosporine, tacrolimus)
- HIV antivirals (e.g. indinavir, ritonavir)
- Anti-epileptics (e.g. phenobarbital, phenytoin).
- Coumarins (e.g. warfarin)
- If enzalutamide is co-administered with warfarin (CYP2C9 substrate), additional INR monitoring should be conducted.
- Medicinal products with a narrow therapeutic range that are substrates for P-gp (e.g., digoxin, colchicine, dabigatran etexilate) or for the breast cancer resistant protein (BCRP) or the multidrug resistance-associated protein 2 (MRP2), should be used with caution when administered concomitantly with enzalutamide and may require dose adjustment to maintain optimal plasma concentrations.
- No other new systemic therapy or new radiotherapy for treatment (exception for spinal cord compression, pain management, etc) for prostate cancer is permitted while subject is on the study. Subjects with pre-existing non-target lesions (e.g., bone metastases) receiving palliative radiography for pain treatment before participation in the study are allowed to continue receiving radiotherapy during the study.

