Subjects who experience a Grade 3 or higher toxicity that is attributed to enzalutamide and cannot be ameliorated by the use of appropriate medical intervention may interrupt treatment with enzalutamide for 1 week or until the toxicity grade improves to Grade 2 or lower severity. Subsequently, study drug dosing may be restarted at the original dose (160 mg/day) or a reduced dose (120 or 80 mg/day) in consultation with the Medical Monitor.

If enzalutamide is co-administered with a strong CYP2C8 inhibitor, the dose of enzalutamide should be reduced to 80 mg once daily. If co-administration of strong CYP2C8 inhibitor is discontinued, the enzalutamide dose should return to the dose used prior to initiation of the strong CYP2C8 inhibitor.

If the adverse event is considered not related to enzalutamide by the Investigator, enzalutamide may be resumed at the same dose.

The Sponsor Medical Monitor may be contacted with any questions or concerns on managing dose.

Seizure Therapy:

Standard anticonvulsant measures, if indicated in the event of a seizure (note: concomitant medication restrictions below).

If the decision is made to continue a subject in the study after a first seizure, treatment including anti-seizure medication may be administered as recommended by the local neurologist and guided by the following restrictions. Enzalutamide has the potential to interact with some anti-seizure drugs.

Seizure Therapy continued:

- Acceptable drugs unlikely to cause interactions are
 - Levetiracetam
 - Gabapentin
 - Pregabalin
- Drugs which are acceptable but **should be administered with caution** include:
 - Ethosuccimide
 - Lacosamide
 - Lamotrigine
 - Oxcarbazepine
 - Topiramate
 - Valproate
 - Zonisamide
- Benzodiazepines **should not be used** for maintenance therapy of seizure.
- Other anti-seizure medications **not permitted in the study** include:
 - Carbamazepine
 - Phenytoin
 - Phenobarbital
 - Primidone
 - Felbamate
 - Vigabatrin
 - Retigabine

Concomitant Medication Restrictions or Requirements:

The following medications are prohibited during the course of the study:

- Therapies to treat prostate cancer including but not limited to:
 - Cytotoxic chemotherapy
 - Hormonal therapies (e.g., anti-androgens, abiraterone acetate, estrogens; testosterone, dehydroepiandrosterone [DHEA], etc.), 5-alpha reductase inhibitors, ketoconazole;

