 - Anticonvulsant substrates of CYP3A4, CYP2C9 or CYP2C19 with a narrow therapeutic index (e.g., carbamazepine, phenytoin, phenobarbital, and primidone);
- Note: GnRH analogues (agonists or antagonists), bone-targeting agents, such as bisphosphonates and denosumab, and glucocorticoids are allowed. Palliative radiotherapy is also allowed (provided the subject does not meet discontinuation criteria).
- Any other investigational agent.

There is a potential for enzalutamide to affect exposures to other medicinal products, or for other

medicinal products to affect exposure to enzalutamide:

- Strong CYP2C8 inhibitors (e.g., gemfibrozil) or inducers (e.g. rifampicin) are to be avoided. If subject must be co-administered a strong CYP2C8 inhibitor, the dose of enzalutamide should be reduced to 80 mg once daily. If a co-administration of the strong inhibitor is discontinued, the enzalutamide dose should be returned to the dose used prior to initiation of the strong CYP2C8 inhibitor.
- Enzalutamide is a strong inducer of CYP3A4 and a moderate inducer of CYP2C9 and CYP2C19. Uridine 5'-diphospho-glucuronosyltransferase (UGT1A1) may also be induced. Medicinal products with a narrow therapeutic range that are substrates of CYP3A4, CYP2C9, CYP2C19, or UGT1A1 should be used with caution when administered concomitantly with enzalutamide and may require dose adjustment to maintain therapeutic plasma concentrations as drug levels may be reduced by the interaction with enzalutamide. Such substrates include, but are not limited to:
 - Macrolide antibiotics (e.g. clarithromycin)
 - Benzodiazepines (e.g. diazepam, midazolam, alprazolam, triazolam)
 - Immune modulators (e.g. cyclosporine, tacrolimus)
 - HIV antivirals (e.g. indinavir, ritonavir)
 - Anti-epileptics (e.g. phenobarbital, phenytoin).
 - Coumarins (e.g. warfarin)
- If enzalutamide is co-administered with warfarin (CYP2C9 substrate), additional INR monitoring should be conducted.
- Medicinal products with a narrow therapeutic range that are substrates for P-gp (e.g., digoxin, colchicine, dabigatran etexilate) or for the breast cancer resistant protein (BCRP) or the multidrug resistance-associated protein 2 (MRP2), should be used with caution when administered concomitantly with enzalutamide and may require dose adjustment to maintain optimal plasma concentrations.

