In a drug-drug interaction study in healthy male volunteers (9785-CL-0006), a single 160 mg oral dose of enzalutamide was administered alone or after multiple oral doses of gemfibrozil (strong CYP2C8 inhibitor). Gemfibrozil increased the composite area under the curve from time zero to infinity ($AUC_{0-\infty}$) of enzalutamide plus N-desmethyl enzalutamide by 2.2-fold with minimal effect on C_{max} ; therefore, strong CYP2C8 inhibitors should be avoided when possible as they can increase plasma exposure to enzalutamide plus N-desmethyl enzalutamide. If coadministration with a strong CYP2C8 inhibitor is necessary, the dose of enzalutamide should be reduced to 80 mg once daily. If coadministration of the strong CYP2C8 inhibitor is discontinued, the enzalutamide dose should be returned to the dose used prior to initiation of the strong CYP2C8 inhibitor. The effects of CYP2C8 inducers on the PK of enzalutamide have not been evaluated in vivo.

In the drug-drug interaction study in healthy male volunteers (9785-CL-0006), a single 160 mg oral dose of enzalutamide was administered alone or after multiple oral doses of itraconazole (strong CYP3A4 inhibitor). Itraconazole increased the composite $AUC_{0-\infty}$ of enzalutamide plus N-desmethyl enzalutamide by 1.3-fold with no effect on C_{max} . As this small change is not clinically meaningful, no starting dose adjustment is needed when coadministering enzalutamide with CYP3A4 inhibitors. The effects of CYP3A4 inducers on the PK of enzalutamide have not been evaluated in vivo.

Additional information on the PK and drug metabolism of enzalutamide is provided in the Enzalutamide Investigator Brochure.

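### The 80 mg rule for strong CYP2C8 inhibitors ignores a dose already reduced for toxicity; a man on 80 mg would get about 2.2 times his intended exposure

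*Protocol*

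**What the plan says.** Protocol 5.1.3 asks sites to avoid strong CYP2C8 inhibitors, then covers the man who has to have one: "If subject must be co-administered a strong CYP2C8 inhibitor, the dose of enzalutamide must be reduced to 80 mg once daily". The synopsis, under Concomitant Medication Restrictions or Requirements, has a softer verb: "If subject must be co-administered a strong CYP2C8 inhibitor, the dose of enzalutamide should be reduced to 80 mg once daily". Sections 5.1.2 and 1.2.2.1 and the synopsis paragraph on dose adjustment also say that "the dose of enzalutamide should be reduced to 80 mg once daily". None of the five statements depends on the dose the man is taking. The rule for stopping the inhibitor does look back to his own dose: "the enzalutamide dose should return to the dose used prior to initiation of the strong CYP2C8 inhibitor".

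A separate rule in 5.1.2 and the synopsis covers Grade 3 or higher toxicity that is attributed to enzalutamide and does not yield to medical management. After an interruption, dosing "may be restarted at the original dose (160 mg/day) or a reduced dose (120 or 80 mg/day) in consultation with the Medical Monitor". For an event judged possibly or probably related, 5.1.2 adds that "enzalutamide may be resumed with medical monitor approval either at the same dose or at a reduced dose of 120 or 80 mg/day".

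No sentence links the two rules. Outside the toxicity restart, contact with the Monitor about dose is optional: "The Sponsor Medical Monitor may be contacted with any questions or concerns on managing dose".

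The basis for 80 mg is in 1.2.2.1. In healthy men given a single 160 mg dose, gemfibrozil raised the composite AUC of "enzalutamide plus N-desmethyl enzalutamide by 2.2-fold", with little effect on the peak.

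**The concern.** The 80 mg figure is a correction for a man on 160 mg: the inhibitor roughly doubles exposure, so the dose is halved. Applied to a man whose dose has already been cut, the same fixed figure does not correct for the inhibitor from his starting point. For a man on 80 mg, a reduction to 80 mg is no reduction at all, although his exposure is expected to rise.

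What is at stake is individual safety. His dose was lowered because of a Grade 3 or higher related toxicity. Following the written inhibitor rule could undo that reduction, and nothing requires the Medical Monitor to look at the dose when the inhibitor is started. A site that sensibly chose 40 mg would be going below every dose the protocol lists and departing from the mandatory wording of 5.1.3. It could then face a reportable incorrect-dose deviation under 8.1.6. The trial also enrolls men with seizure risk factors who were kept out of earlier studies, and 7 of 800 men had a seizure at 160 mg in the Phase 3 study described in 1.3.

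**Working it through.** **Inputs from the Protocol**
- Full dose 160 mg/day; doses allowed after toxicity 160, 120 or 80 mg/day (5.1.2).
- Dose with a strong CYP2C8 inhibitor: 80 mg (5.1.2, 5.1.3, 1.2.2.1, synopsis).
- Exposure ratio r = 2.2 for parent plus active metabolite (1.2.2.1).
- No major departure from dose proportionality between 30 and 600 mg, and a nearly flat steady-state profile (1.2.2.1). This makes average exposure a reasonable scale and allows it to be expressed as an equivalent daily dose without inhibitor.
- Capsule strength 40 mg (5.1.1); maximum tolerated dose 240 mg (1.2.2).

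**Assumption.** The ratio at steady state in patients is not given. A range of 1.5 to 2.5 is used.

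**Step 1: reproduce the plan's figure.** Matching dose = current dose / r. For a man on 160 mg, 160 / 2.2 = 73 mg, and the nearest capsule dose is 80 mg. The rule is right for him.

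**Step 2: apply the same formula to a reduced dose.** 120 / 2.2 = 55 mg; 80 / 2.2 = 36 mg. Both lie below 80 mg.

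**Step 3: exposure under the rule as written.** Equivalent dose = 80 × r: 80 × 1.5 = 120; 80 × 2.2 = 176; 80 × 2.5 = 200 mg. Divided by the dose before the inhibitor:

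| Dose before inhibitor | r = 1.5 | r = 2.2 | r = 2.5 |
|---|---|---|---|
| 160 mg | 0.75 | 1.10 | 1.25 |
| 120 mg | 1.00 | 1.47 | 1.67 |
| 80 mg | 1.50 | 2.20 | 2.50 |

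The man on 80 mg is above his intended exposure across the whole range. The man on 120 mg is on target at 1.5 and about half as high again at 2.2.

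**Step 4: would 40 mg be better?** At r = 2.2, 40 mg gives 40 × 2.2 = 88 mg-equivalent: 88 / 80 = 1.10 for a man on 80 mg and 88 / 120 = 0.73 for a man on 120 mg. At r = 1.5 it gives 60: 60 / 80 = 0.75 and 60 / 120 = 0.50. The 40 and 80 mg doses are equally far from target where:
- on 80 mg: 80 − 40r = 80r − 80, so r = 1.33;
- on 120 mg: 120 − 40r = 80r − 120, so r = 2.0.

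So 40 mg is the closer dose for the 80 mg man throughout the assumed range, and for the 120 mg man only if r exceeds 2.0.

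**Step 5: absolute level.** 176 / 160 = 1.10 and 176 / 240 = 0.73. The level is 10% above full dose and 27% below the maximum tolerated dose.

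**Step 6: men affected.** The documents give no rates. Assuming that 5% to 15% of 400 are reduced for toxicity and 0.5% to 2% of those later start a strong inhibitor: 400 × 0.05 × 0.005 = 0.1 and 400 × 0.15 × 0.02 = 1.2 men.

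**The case against.** The strongest objection is that the case is rare and partly covered already. Strong inhibitors are to be avoided. The Monitor is involved in every toxicity restart, so knows who the reduced men are, and can be consulted on any dosing question. Concomitant medication is recorded at each visit. A recurrence of Grade 3 toxicity would bring the interruption rule into play again, and 6.1 removes a man for whom continued dosing would be an undue risk. All of this stands, and it limits how much the point matters. It does not close the gap: avoidance is followed at once by a provision for co-administration, Monitor contact at that moment is optional, and the other safeguards act only after exposure has risen or harm has appeared.

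A reader might infer more than the documents support:

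- **That the protocol uniformly orders this dose.** Only 5.1.3 says must; the other four statements say should. For a man already on 80 mg, the instruction to reduce to 80 mg describes no possible action.
- **That every dose-reduced man is clearly overexposed.** For a man on 120 mg this depends on the ratio, and 2.2 comes from one single-dose study in healthy men.
- **That a hold or 40 mg should be mandatory.** Step 4 shows that 80 mg is the closer dose for a man on 120 mg when the ratio is below 2.0.
- **That the level is dangerous in itself.** It is below the maximum tolerated dose, and 1.3 reports no seizures at 240 mg or below in the dose-escalation study. That comfort is limited in men with seizure risk factors, but it rules out calling the level extreme.
- **That 5.1.2 conflicts with itself when the inhibitor is stopped because of related toxicity.** Monitor approval already governs a restart after related toxicity, and the return to the prior dose is only a should. The two can be read together.

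**Conclusion.** The point holds as a narrow patient-safety gap. One fixed dose is given whatever the current dose, and for a man already reduced to 80 mg it leaves about 176 mg-equivalent, or 2.2 times his intended exposure (1.5 to 2.5 times over the assumed range). For a man on 120 mg it gives about 1.5 times at a ratio of 2.2 and could be about right at 1.5. The result rests on the single-dose, healthy-volunteer ratio carrying over to daily dosing and on the dose proportionality reported in 1.2.2.1.

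The number affected is probably around one man or none, on rates that are assumptions. The sample size and primary analysis do not change. This is a cheap improvement, not a flaw in the design.

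**What to change.** Add one sentence to 5.1.2, 5.1.3 and the synopsis:

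> *A subject already reduced to 120 or 80 mg/day for toxicity must not start a strong CYP2C8 inhibitor without prior Medical Monitor approval of the enzalutamide dose (including the option to hold or to give less than 80 mg/day) for the period of co-administration.*

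This leaves the choice between 80 mg, a lower dose and a hold to someone who can weigh the toxicity, the need for the inhibitor and the risk of underdosing. It also makes a dose below 80 mg permissible under the protocol. The 80 mg rule for men on 160 mg stays as it is.

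The cost is one extra Monitor contact in a rare case. Capsules are already 40 mg, so no new strength, visit, data item or patient is needed.

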1.2.2.1 Pharmacokinetics and Drug Metabolism

In PK investigations in men with CRPC, enzalutamide was absorbed rapidly after oral administration, with the time to maximum plasma concentration (t_{max}) after a single dose typically occurring at 1 hour post dose. No major deviations from dose proportionality were observed over the dose range 30 mg to 600 mg.

Terminal half-life was approximately 5.8 days. The average difference between the peak (maximum plasma concentration, C_{max}) and trough (predose plasma concentration, C_{trough}) concentrations was $\leq 25\%$. Therefore, plasma profiles at steady state resembled a constant

infusion. Time-linear PK was observed beyond steady state at Day 28. Plasma concentrations of enzalutamide and the active metabolite, N-desmethyl enzalutamide, were approximately the same.

In a drug-drug interaction study in male patients with CRPC (9785-CL-0007), a single oral dose of a substrate for cytochrome P450 (CYP) 2C8, CYP2C9, CYP2C19, or CYP3A4 was administered before and concomitantly with enzalutamide (after at least 55 days of dosing at 160 mg daily). Enzalutamide at steady state reduced the plasma exposure to midazolam (CYP3A4 substrate), warfarin (CYP2C9 substrate), and omeprazole (CYP2C19 substrate) by 86%, 56%, and 70%, respectively. Based on the magnitude of the decreases in exposure, enzalutamide is considered a strong inducer of CYP3A4 and a moderate inducer of CYP2C9 and CYP2C19. Substrates of CYP3A4, CYP2C9, and CYP2C19 with a narrow therapeutic index should be avoided when possible, as enzalutamide may decrease plasma exposure of these drugs. If enzalutamide is coadministered with warfarin (CYP2C9 substrate), additional international normalized ratio (INR) monitoring should be conducted. Enzalutamide did not cause clinically meaningful changes in exposure to pioglitazone (CYP2C8 substrate).

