6 DISCONTINUATION

6.1 Discontinuation of Individual Subject(s)

A discontinuation is a subject who enrolled in the study and for whom study treatment is permanently discontinued for any reason.

Subjects who are continuing to receive clinical benefit from treatment with enzalutamide and have not met any discontinuation criteria may transition to an open label extension study upon approval of the study protocol at the institution they are receiving treatment at. The subject is free to withdraw from the study treatment and/or study for any reason and at any time without giving reason

for doing so and without penalty or prejudice. The Investigator is also free to terminate a subject's involvement in the study at any time if the subject's clinical condition warrants it.

If a subject is discontinued from the study with an ongoing adverse event or an unresolved laboratory result that is significantly outside of the reference range, the Investigator will attempt to provide follow-up until the condition stabilizes or no longer is clinically significant.

The following safety/compliance events will result in the removal of subjects from enzalutamide therapy and from the study if:

- Any adverse event that is intolerable to the subject and that cannot be ameliorated by the use of adequate medical intervention, or that in the opinion of the Investigator would lead to undue risk to the subject if dosing continued;
- Any first confirmed seizure requiring treatment with maintenance anticonvulsant therapy if the only anticonvulsant(s) the patient can tolerate is carbamazepine, phenytoin, phenobarbital, primidone, felbamate, vigabatrin, or retigabine.
- Any second seizure confirmed by independent adjudication committee;
- Inability to maintain the absolute neutrophil count above 500/ μ L (Grade 4) or 500-1000/ μ L (Grade 3) with evidence of infection;
- Inability to maintain the platelet count above 25,000/ μ L (Grade 4) or 25,000-50,000/ μ L (Grade 3) with spontaneous bleeding;
- Subject who has unequivocal evidence of disease progression (upon bone disease progression per PCWG2 guidelines or soft tissue disease progression per RECIST 1.1) or is no longer deriving clinical benefit;
- Subject who is, in the opinion of the Investigator or the Medical Monitor, grossly non-compliant with the protocol's requirements.

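### Protocol section 5.1.3 and the synopsis list phenytoin and phenobarbital both as prohibited and as drugs to use with caution; the wording needs reconciling, though the primary estimate does not depend on it

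*Protocol*

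**What the plan says.** Section 5.1.3 of the protocol opens with medications barred during the study. Among them it states: "carbamazepine, phenytoin, phenobarbital, and primidone are not permitted in this study". Further down, the section turns to interactions and says that narrow-range substrates of UGT1A1 and of three CYP enzymes "should be used with caution when administered concomitantly with enzalutamide and may require dose adjustment to maintain therapeutic plasma concentrations". The examples under that sentence include "Anti-epileptics (e.g. phenobarbital, phenytoin".

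The synopsis, under concomitant medication restrictions, has the same pair. Its prohibited list contains "Anticonvulsant substrates of CYP3A4, CYP2C9 or CYP2C19 with a narrow therapeutic index (e.g., carbamazepine, phenytoin, phenobarbital, and primidone", and its caution list again names phenobarbital and phenytoin.

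Section 1.2.2.1, which is background, says that narrow-index substrates of CYP3A4, CYP2C9 and CYP2C19 "should be avoided when possible, as enzalutamide may decrease plasma exposure of these drugs". It names no anti-epileptic.

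The sections that deal with a man after a seizure take one line. Section 4.1.3 puts both drugs in its not-permitted list, and section 4.2 says they are not permitted. Section 6.1 removes a man whose first confirmed seizure requires maintenance anticonvulsant therapy "if the only anticonvulsant(s) the patient can tolerate is carbamazepine, phenytoin, phenobarbital, primidone, felbamate, vigabatrin, or retigabine". The matching synopsis paragraphs agree.

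**The concern.** A drug cannot be both barred and allowed with caution. The caution line also has no evident use in eligible men. Exclusion criterion 3 keeps out men currently on anti-epileptics, and inclusion criterion 8a requires 12 months without anticonvulsants in men with a seizure history. The line could therefore apply only to a drug started on study, most plausibly after a seizure.

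That is a sensitive moment. The protocol lets men continue enzalutamide after a first confirmed seizure, with an allowable anticonvulsant if needed. Section 4.1.3 also refers the reader to the concomitant medication restrictions, which is where the two instructions collide. A site that acts on the caution sentence gives a drug that the rest of the protocol excludes, and records a PD4 deviation while following protocol text.

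**Working it through.** **Where the two drugs, or their substrate class, are addressed**

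| Place | Instruction |
|---|---|
| 5.1.3, prohibited list; synopsis counterpart | Not permitted |
| 5.1.3, interaction list; synopsis counterpart | Use with caution, dose may need adjusting |
| 1.2.2.1 (class only, drugs not named) | Avoid when possible |
| 4.1.3; synopsis, seizure therapy | Not permitted; absent from that section's own caution list |
| 4.2; synopsis, suspected seizure management | Not permitted |
| 6.1; synopsis, discontinuation criteria | Among the seven drugs in the removal rule |

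The direct conflict is confined to 5.1.3 and its synopsis counterpart.

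**What follows for a man after a first confirmed seizure**

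1. Removal under 6.1 needs two things together: maintenance therapy is required, and the only anticonvulsants he can tolerate are among the seven named drugs.
2. Section 4.1.3 lists ten other drugs as acceptable, three as unlikely to interact and seven with caution. A site applying the prohibition can therefore keep a man on study with one of those.
3. If a site instead gives phenytoin or phenobarbital on the strength of the caution line, PD4 (excluded concomitant treatment; protocol 7.8 and 8.1.6, SAP 7.2.2) applies. PD4 does not depend on the 6.1 conditions.
4. If the 6.1 conditions are also met and he stays on, PD2 (withdrawal criterion met, not withdrawn) applies too.

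**How many men**

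The planning rate in section 7.1 reproduces: 2.8 per 100 patient-years × 4/12 year = 0.93 per 100, so 0.93%. The exact binomial probability of 5 or fewer events with n = 350 and p = 0.0093 is 88.9%, as stated.

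Expected men with a seizure in 4 months:

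- Section 7.1, 0.93%: 0.0093 × 350 = 3.3
- Synopsis, 0.9%: 0.009 × 350 = 3.2
- SAP section 4, 1%: 0.01 × 350 = 3.5

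This counts every man with a seizure. The documents do not say for what fraction either drug would be considered, so about 3 is a ceiling on the expected number affected in that period. The 5 of 350 in the sample-size text illustrates interval width and is not an expected count.

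**Effect on the seizure estimates**

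- Primary proportion: a confirmed seizure in the 4-month period makes the man evaluable and counts him once, whether he is then kept or removed. For example, 5/350 = 1.43% on either reading.
- First-event incidence and Kaplan-Meier (SAP 7.5.1.2): only the first seizure counts, and it precedes any choice of anticonvulsant for it. Later seizures are listed.
- Patient-time: the SAP does not say whether exposure stops at the first seizure. If it does, nothing changes. If all exposure were counted, the 4-month denominator could move by at most 3.3 men × 4/12 = 1.1 of 350 × 4/12 = 116.7 patient-years, which is 0.9% of it.

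**The case against.** The strongest reply is that the protocol is clear where it matters. The caution line sits in a general interaction list beside macrolides, HIV antivirals and coumarins. To act on it, a site would have to overlook the prohibition earlier in the same section as well as 4.1.3, 4.2 and 6.1. On this view the deviation argument is circular, since PD4 arises only because the rest of the protocol excludes the drug.

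Most of this stands, and it limits the point. A reader might infer that the same man would be removed at one site and kept on enzalutamide at another. The documents do not set those two outcomes. The post-seizure sections agree with each other, and removal needs the narrow 6.1 conditions. Different handling between sites is possible through a misreading, but it is not a necessary result of the plan.

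What does not stand is that the line is harmless. If the prohibition prevails, the caution wording is misleading in a safety instruction, and it appears twice in current text. The prohibition is also easy to miss: it is nested under therapies for prostate cancer, and in 5.1.3 it follows an unclosed parenthesis.

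**Conclusion.** The inconsistency is real, of low severity, and a matter of wording. It concerns two of the seven anticonvulsants named in 6.1.

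On the planning rate it could touch at most about 3 expected men in the 4-month period, and probably fewer. Three assumptions lie behind that figure: the planning rate, which comes from previous studies, holds in this population; 350 men are evaluable; and either drug would be started only for a seizure that is later confirmed. Men treated for a suspected seizure that is not confirmed would add to it. The documents give no planned extension exposure from which to put a figure on the later period.

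Because the affected men are those with the primary event, a reader might also infer that the seizure estimate is at risk. It is not: the primary proportion and the first-event incidence are the same on either reading, the latter on the usual convention that patient-time stops at the first event. What could vary is patient safety after a seizure, exposure after it, the listing of later seizures, and the counts of discontinuations and of PD4 and PD2 deviations.

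**What to change.** Reconcile section 5.1.3, section 1.2.2.1 and the synopsis text on concomitant medication with sections 4.1.3, 4.2 and 6.1 and the synopsis paragraphs on seizure therapy, suspected seizure management and discontinuation. Each named anti-epileptic should appear under one instruction only. Make PD4 (protocol 7.8 and 8.1.6) and the 6.1 criterion refer to that single list. Which instruction is right is for the sponsor's clinical team to decide.

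The cost is a wording change sent to sites with the next amendment. No data collection or analysis changes. SAP 7.2.2 takes its deviation definitions from protocol section 8.1.6, so it would follow without its own revision.
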